## 1.2 Rationale

It is recognized that SARS-CoV-2 will transmit differently in African settings, and that risk factors for infection and mild or severe disease may be different to higher income settings. Understanding transmission and identifying at-risk populations is urgent for African countries, who need to target scarce resources as effectively as possible to interrupt transmission and protect vulnerable risk groups.

Box. The epidemiological situation in Mozambique on 29/09/2020.

The SARS-CoV-2 outbreak is still accelerating in Mozambique, as indicated by both the trend in the number of reported cases and the positivity rate. 7983 SARS-CoV-2 infected cases were reported, including 295 imported cases, and 58 deaths. Since the start of the outbreak, 134,011 suspected cases have been tested. In September 2020, consistently more than half of new cases were reported in Maputo City. In Maputo City a total of 3,427 cases and 38 deaths have been reported. The average number of new daily cases reported went from 47 in the first week of September, to 97 in the week up to 26/09. A sero-prevalence survey undertaken in the last two weeks of August 2020, found an overall seroprevalence of 3.8% in Mauto city, with only slight variation between age groups (range 3.0% in 35-59 year olds to 4.5% in  $\geq 60$  year olds). Nevertheless, the latter age group accounts for the majority of hospitalisations. Of all cases reported in Mozambique, 56% were asymptomatic, 37% have a mild symptomatology, 6% moderate symptomatology and 1% a severe symptomatology. 42% of the infected individuals are female.

We aim to determine robust transmission parameters of SARS-CoV-2 to understand infectiousness and epidemic spread. We will investigate risk factors for infection and severe disease, assess impact of vaccines / behavioral interventions on transmissibility and infectiousness, and explore the role of certain age groups, societal activities, pre- and asymptomatic infections in transmission in a peri-urban area of Maputo, Mozambique. By building on an existing health and demographic surveillance system (HDSS) it will be highly feasible to expand the existing population-based surveillance with biweekly home visits, viral RNA and serological testing. For serological testing, a newly validated SARS-CoV-2 antibody assay will be added to the capacity at INS. This will provide high quality, timely, unbiased epidemiological data and indicators on the natural history and key SARS-CoV-2 transmission parameters, which can be rapidly collected and analysed, informing the country's response, as well as that of other African countries.

Since the number of cases started to accelerate in September 2020, we aim to have a first analysis point at 3 months after the implementation of the project in the HDSS, to estimate the progression of the pandemic in the community and help plan for effective and feasible control measures.

## 2. Study Objectives

### Primary objectives

- Estimate the attack rate, infection fatality, serial interval, and reproduction number of SARS-CoV-2 infection in peri-urban Maputo.
- Estimate the proportion of infections that are asymptomatic, and tease out the role these play in transmission.

- Estimate the incidence rate of SARS-CoV-2 infection, COVID-19 disease (symptomatic infection), rate of severe COVID-19 disease, hospitalization for medical care and mortality, over a 12 month period in peri-urban Maputo.
- Identify risk factors for SARS-CoV-2 infection and for severe COVID-19 disease, which could include reported HIV status, nutritional status, blood group, underlying co-morbidities, household factors, pre-existing levels of anti-alphacoronavirus antibodies (CoV 229E, NL63) or anti-betacoronavirus antibodies (CoV OC43 and HKU1), and availability and adoption of measures aimed to reduced transmission.
- Create social contact matrices that can be used to parametrize dynamic transmission models.
- Estimate the household secondary infection rate

#### Secondary objectives

- Measure antibody titers over time and analyze the correlation between anti-coronavirus (endemic coronavirus or SARS-CoV-2) antibody titers and reinfection
- Assess the individual uptake of measures aimed to reduce transmission and assess barriers to uptake (absence soap/water, income loss, ability to self-isolate, availability of masks, distrust, lack of understanding of the communication)
- Derive and validate a clinical prediction rule for SARS-CoV2 infection
- Geographical mapping of clusters, spread and identification of transmission hotspots.
- Sequence selected strains of SARS-CoV-2
- Understand non-SARS-CoV-2 etiologies of respiratory disease in the study population.
- Identify factors associated with household SARS-CoV-2 infection and with household infection resulting in Covid19 disease, including viral load and symptoms of household index case, household and individual characteristics and behaviour to prevent infection.
- Estimate total brand-specific vaccine effectiveness (among vaccinees) against PCR confirmed SARS-CoV-2 clinical infection.
- Estimate total brand-specific vaccine effectiveness (among vaccinees) against SARS-CoV-2 seroconversion
- Estimate overall and brand-specific vaccine effectiveness (total among vaccinees and indirect among non-vaccinated) against PCR confirmed SARS-CoV-2

Table 1. Study activities and outcome measures. Primary outcome measures in **bold**.

Planned activities	Sampling strategy and sample size	Outcome measures
Active syndromic population surveillance (biweekly) with PCR testing of symptomatic individuals – 12 months	15393 individuals (2108 households) Possible cases reporting any respiratory sign or loss of smell or taste, with or without fever, selected for PCR testing. Initially, before widespread community transmission, pooled testing of possible cases; when >50 confirmed cases per week, switch to PCR testing of 1 in 10 possible cases (systematic selection - every 10th possible case)	
 
● COVID-19 disease incidence rate (symptomatic infections per person-month)
 
● COVID-19 related hospitalisation rate
 
● Case (disease) fatality risk (%)
 
● Risk factors for severe outcome/hospitalization
 
● Basic reproduction number
 
● Effective reproduction number
 
● Serial interval
 
● Proportion uptake of measures to prevent infection; barrier uptake
 
● Effectiveness of interventions
 

		
 
• COVID-19 incidence density maps
 
• COVID-19 likelihood ratios of clinical signs
 
• Brand-specific vaccine effectiveness against confirmed COVID-19 (disease)
 

Age-stratified sero-survey at 0, 3, 6, 12 months	2400 individuals/dried blood spot samples per round (800 per age group <18yo, 18-50 yo, >50yo) An age stratified sample of individuals will be selected (simple random sample in each age group)	
 
• SARS-CoV-2 infection annual attack rate (%)
 
• Infection fatality risk
 
• Proportion asymptomatic infections, by age group
 
• Risk factors for infection
 
• Association between antibody titers and reinfection
 
• Brand-specific total vaccine effectiveness against SARS-CoV-2 seroconversion
 
• Overall vaccine effectiveness against SARS-CoV-2 seroconversion
 

Repeated social mixing survey	the same 2400 individuals selected for the sero-survey (800 per age group <18yo, 18-50 yo, >50yo)	
 
• correlation between number of contacts, intensity of contacts and attack rate
 
• correlation between uptake of control measures and attack rate
 
• social contact matrices to be used to parametrize dynamic transmission models
 

Household contact investigation at 1 day after confirmation of the household index case and 28 days after index case symptom onset	First 100 households with $\geq 1$ confirmed case; median household size 7.3 $\Rightarrow 100*6= 600$ household contacts	
 
• Household secondary infection rate
 
• Risk factors for household infection
 
• Risk factors for household infection resulting in Covid19 disease
 
• Total vaccine effectiveness against COVID-19
 

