The repeated sero-survey, collecting dried blood spots through a finger prick, will be added to the biweekly household visits at 3, 6 and 12 months after COVID-19 local transmission is confirmed. During four other biweekly household visits, the participants selected for the sero-survey will also be interviewed on contact and mobility patterns during the previous day, and uptake of COVID-19 control measures, using the 'Social mixing questionnaire'. Its timing will depend on the stage of the outbreak:

1. shortly after the baseline interview (second visit),
2. when local transmission is well established and the number of new cases is increasing,
3. a month after an initial peak, when the number of new cases is decreasing,
4. during the final study visit.

Table 4 . Forms completed during each study activity

Planned activities	Sample size	Research form
Baseline household visit	15393 individuals (2108 households)	
 
· Informed consent form for population-based COVID-19 surveillance (with household head)
 
· Informed consent form for serial sero-survey (with selected individual)
 
· Baseline household visit form
 

Active syndromic population surveillance	15393 individuals (2108 households) visited every 2 weeks	
 
· Household follow-up visit form
 

Swabbing & PCR testing of symptomatic individuals	possible cases from the surveillance population; initially pooled testing of possible cases; when >50 confirmed cases per week, switch to PCR testing of 1 in 10 suspected cases	
 
· Possible case report form
 
· Possible case lab request and result form
 

Follow-up of PCR confirmed cases at day 28 and day 56 past symptom onset	PCR confirmed cases from the surveillance population	
 
· Confirmed case follow-up form
 

Age-stratified sero-survey at 0, 3, 6, 12 months	2400 individuals/serum samples per round (800 per age group <18yo, 18-50 yo, >50yo NOTE: this is budget dependent, pending cost of	
 
· Sero-survey form
 
· Sero-survey lab request and result form
 

	assay, might be decreased to 1600, spread over two age strata)	
Social mixing survey	the same 2400 individuals selected for the sero-survey; during different HH visits than sero-survey visits	· Social mixing questionnaire

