## 7. Statistical Analyses

### 7.1 Methods

All estimated transmission or clinical outcome indicators will be adjusted for the design effect, related to the selection of HDSS enumeration areas (clusters) within the source populations. Intraclass correlation coefficients can be deducted from previous studies in the HDSS. The results of the sero-survey and social mixing survey will additionally be adjusted for age-stratified sampling.

We will calculate a incidence rate of COVID-19 disease throughout one year, adjusting for the sensitivity of SARS-CoV-2 RT-PCR on nasal swabs by delay between symptom onset and testing. Using the longitudinal sero-survey data, determining the proportion of asymptomatics, we will be able to adjust the clinical incidence rate to a SARS-CoV-2 infection incidence rate, and determine the SARS-CoV-2 infection annual attack rate and the infection fatality risk by age group.

We will undertake three risk factor analyses: of SARS-CoV-2 infection, of COVID-19 disease (symptomatic infection), and of COVID-19 hospitalisation and death (severe disease). Using negative binomial regression, we will investigate the association with socio-demographic factors, clinical characteristics such as underlying medical conditions, and uptake of preventive measures. We also investigate the association between SARS-CoV-2 infection (from the sero-survey) and recent exposure, contact and mobility patterns (from the social mixing questionnaire).

We will assume everyone will be susceptible initially and basic and effective reproductive numbers ( $R_0$  and  $R_e$ ) will be calculated by the rate of change of incidence over successive serial intervals (time between onset of infection of index and onset of infection of infected).

We will use established methods (Cauchemez et al 2004; te Beest et al 2013) to estimate generation time distribution, ratio of transmissibility between symptomatic and asymptomatic cases, duration of

the infectious period, and the basic reproduction number, from the transmission data collected in households.

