## 7.2 Sample size and power

Assuming a 40% annual attack rate, 50% symptomatic infections (cases), 2% overall case fatality risk, of which 90% are identified by the active population surveillance, 2790 COVID-19 cases and 56 deaths will be identified through the study period. The average incidence rate of the HDSS population would then be 1.50 cases per 100 person months with lower and upper 95% confidence interval limits 1.45 and 1.56. The overall case fatality risk would have as lower and upper 95% confidence interval limits at 1.53 and 2.58%.

To determine the infection attack rate from a simple random population sample of three age strata (comparable in size), with +/-3% confidence limits, 95% confidence interval, assuming the attack rate may reach 40% towards the end of the study period, samples from 800 individuals per age stratum per round will need to be collected.

Assuming the household secondary attack rate to be close to 17% (Fung et al, Clin Infect Dis, 2020) and a median household size of 7.3 (based on HDSS data), a 5% confidence limit and a design effect of 3, 642 household members will need to be enrolled, or 100 households. The WHO also recommended to include 100 households in household transmission investigations.

Assuming 20% vaccination coverage among the 2400 sero-survey participants, 5% of sero-conversion over 3 months and 10% of seroconversion over 6 months, a 95% two-sided confidence interval and an anticipated crude total vaccine effectiveness of 50%, there will be 66% power to observe this effect after 3 months and 97% power after 6 months.

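### PCR testing drops to 1 in 10 above 50 confirmed cases a week, yet the incidence interval in section 7.2 counts all 2,790 cases and section 7.1 names no adjustment for the testing fraction

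*Combined protocol and SAP*

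**What the plan says.** - **Testing rule.** Table 1 (section 2), in the row that carries the bolded disease incidence rate: "when >50 confirmed cases per week, switch to PCR testing of 1 in 10 possible cases (systematic selection - every 10th possible case". Table 4 (section 5.1): "when >50 confirmed cases per week, switch to PCR testing of 1 in 10 suspected cases".
- **Planned yield and precision.** Section 7.2 expects that "2790 COVID-19 cases and 56 deaths will be identified through the study period" and gives an incidence of "1.50 cases per 100 person months with lower and upper 95% confidence interval limits 1.45 and 1.56". On fatality it says: "The overall case fatality risk would have as lower and upper 95% confidence interval limits at 1.53 and 2.58" (per cent). It does not mention the testing rule.
- **Planned adjustments.** Section 7.1 will estimate disease incidence "adjusting for the sensitivity of SARS-CoV-2 RT-PCR on nasal swabs by delay between symptom onset and testing". It also names a design effect for enumeration areas and a correction for the asymptomatic proportion. On sampling it says: "The results of the sero-survey and social mixing survey will additionally be adjusted for age-stratified sampling". Nothing covers the fraction of possible cases tested, and the analytical methods in the Synopsis add nothing.
- **Reproduction number.** Under 7.1, R0 and Re "will be calculated by the rate of change of incidence over successive serial intervals", alongside a separate household-based estimate.
- **Full testing elsewhere.** Section 3 describes a specimen and PCR for any symptomatic person throughout the 12 months. Table 2 budgets 8,000 swabs for PCR from 8,000 possible cases.

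**The concern.** The sampling rule and the precision statement describe different studies. One confirms every identified case; the other confirms a tenth of them for most of the epidemic. Disease incidence is a primary outcome, so its stated precision should be what the design delivers.

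The present text also does not allow the right weight to be written down. Section 5.1 requests PCR results already obtained at health facilities, and section 4.2 tests symptomatic household contacts whenever symptoms appear. Neither says whether the 1-in-10 selection applies to these people. If they are always tested, a blanket weight of 10 overcounts them.

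The trigger is a confirmed count that the rule itself reduces up to tenfold, and no condition for returning to full testing is given. A mid-epidemic change in ascertainment falls directly on the incidence series behind incidence-based Re, the incidence maps and vaccine effectiveness against disease.

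**Working it through.** **1. Reproduce section 7.2.** Inputs: 40% attack rate, 50% symptomatic, 90% identified, 12 months.
- Cases: 15,500 × 0.40 × 0.50 × 0.90 = 2,790. The stated population of 15,393 gives 2,771, which is close enough.
- Rate: 2,790 / (15,500 × 12 = 186,000 person-months) = 1.50 per 100.
- Exact Poisson 95% interval for a count of 2,790: 1.445 to 1.557. This matches the stated 1.45 to 1.56, with no testing fraction and no design effect.

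**2. Is the trigger reached?** 2,790 / 52 = 53.7 a week (53.3 from 2,771). A year with no week above 50 holds at most 50 × 52 = 2,600 cases. If all 2,790 are confirmed, at least one week must exceed 50 whatever the shape of the wave.

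**3. Confirmed cases under the rule.** Assumption: one normal-shaped wave centred in 52 weeks, with the switch in the week after the first week above 50. Either the switch is permanent, or full testing resumes in the second week after the last week above 50.

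| SD (weeks) | Peak per week | Weeks above 50 | Confirmed, permanent switch | Confirmed, full testing resumes |
|---|---|---|---|---|
| 4 | 276 | 14 | 445 | 502 |
| 6 | 185 | 20 | 446 | 530 |
| 8 | 139 | 22 | 543 | 709 |
| 10 | 112 | 26 | 559 | 751 |
| 12 | 96 | 28 | 600 | 835 |

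For SD 4 with a permanent switch, about 184 cases arise before it and 2,606 after: 184 + 2,606/10 = 445. After the switch the raw confirmed count peaks at only 10 to 28 a week across these waves.

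**4. Interval with correct weighting.** Let c be weekly cases, f the fraction tested and p the positivity.
- *Inverse testing fraction:* variance = Σ c/f. For SD 4, 184 + 10 × 2,606 = 26,244, and √(26,244/2,790) = 3.07 times the stated standard error. Half-width = 1.96 × √26,244 / 1,860 = 0.17, giving 1.33 to 1.67. For SD 12 with full testing resumed the ratio is 2.83, giving 1.34 to 1.66.
- *Possible cases times positivity:* variance = Σ [c + (1/f − 1)·c·(1 − p)]. With constant p = 2,790/8,000 = 0.349 and SD 4: 2,790 + 9 × 2,606 × 0.651 = 18,059, ratio 2.54, interval 1.36 to 1.64. With a flat background of non-COVID episodes the ratio falls to as little as 1.94, interval 1.39 to 1.61.

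**5. Routes that are always tested (assumed shares of cases).** At 5%, 560 to 930 are confirmed; at 10%, 680 to 1,030. With the weight of 10 restricted to selected cases, the ratio is 2.70 to 3.00 (1.35–1.65 at the narrowest). By the positivity method it is 1.92 to 2.51. A blanket weight of 10 would overstate incidence 1.35 to 1.42 times (5%) or 1.70 to 1.84 times (10%).

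**6. Clustering.** Steps 1 and 4 both leave it out. If clustering multiplied the case variance by an assumed 2 or 3, the ratio r becomes √((r² + 1)/2) = 1.5 to 2.3, or √((r² + 2)/3) = 1.4 to 2.0.

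**7. Case fatality.** The Jeffreys interval for 56/2,790 is 1.54 to 2.58%, within rounding of the stated interval. If only deaths among tested cases count, 8.9/445 gives 0.99 to 3.63% and 16.7/835 gives 1.21 to 3.12%. If all 56 deaths are found and only the denominator is estimated, it is about 1.51 to 2.67%.

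**8. Specimens tested.** About 1,280 to 4,450, against 8,000 in Table 2 (8,000 possible cases including COVID-19, no always-tested route).

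**9. If no weight were applied.** 445/186,000 to 835/186,000 = 0.24 to 0.45 per 100 person-months.

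**The case against.** **The interval is not a calculation error, and the bias is hypothetical.** Correct. Section 7.2 computes its interval properly for a full count. Selection is systematic with a known fraction, so incidence stays estimable, and 7.1 does not plan an unweighted analysis. An interval of 1.33 to 1.67 is about ±11% on a descriptive rate. What stands is that even correct weighting cannot deliver 1.45 to 1.56, and that the weight cannot be specified until the always-tested routes are named.

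**The trigger may not be reached.** Section 7.2 counts identified cases, whereas the trigger counts confirmed ones. With PCR sensitivity of 60 to 90% (assumed), the flat mean is 32 to 48 a week. The assumed waves still exceed 50 in 12 to 26 weeks. The vaccine paragraph in 7.2 uses 5% seroconversion over 3 months, which implies 15,500 × 0.05 × 0.45 / 13 ≈ 27 cases a week. At the corresponding 20% a year, waves of SD 4 to 10 weeks still cross 50; at SD 12 the peak is 48. The trigger is missed only if the attack rate stays below about 7% (SD 4) to 21% (SD 12), and the incidence calculation assumes 40%.

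**R0 is largely protected.** This is fair. Early growth precedes the switch, and R0 is also estimated from households. The exposed quantity is incidence-based Re around the switch.

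**The switch may be one-way.** On that reading no return rule is needed, but the text should say so.

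**Deaths may be found anyway.** Section 4.1 describes continuous reporting of deaths in the surveillance site, which favours the narrow fatality interval. Table 2, note 3, limits outcome follow-up to confirmed cases, so this is unsettled.

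**Table 2 is only an estimate.** It is footnoted as such and section 3 is a summary, but both still read as full testing.

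**Conclusion.** The concern holds. The expected cases and incidence interval in 7.2 assume full confirmation, the tables prescribe 1-in-10 testing at an incidence the plan itself assumes, and 7.1 has no step to connect the two. With correct weighting the incidence interval is 1.9 to 3.1 times as wide as stated, or 1.4 to 2.3 times if clustering doubles or triples the variance. About 445 to 835 cases would be confirmed instead of 2,790, or up to 1,030 if a tenth are always tested.

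These sizes rest on assumed single waves, assumed always-tested shares and the 40% attack rate in 7.2. That 7.2 does not match the rule does not depend on the shape of the wave, provided the identified cases are confirmed. The fatality interval may be much wider or almost unchanged, depending on how deaths are found. The sero-survey attack rate and the household-based reproduction number do not depend on this series.

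**What to change.** 1. **Section 7.1.** State, for each entry route, whether the 1-in-10 selection applies. After the switch, estimate weekly cases as possible cases subject to selection times positivity among those selected, or apply the inverse testing fraction to selected cases only. Add cases tested regardless of selection at weight 1 and keep them out of the positivity estimate. Include the sampling step in the variance. Use this series for incidence, incidence-based R and the maps; for vaccine effectiveness against disease, use case weights or adjust for calendar time.
2. **Trigger.** Define the switch, and any return to full testing, on the weighted estimate and not on the raw confirmed count. If the switch is permanent, say so.
3. **Section 7.2.** Restate the expected confirmed cases and the incidence and fatality intervals under the rule, with the assumed epidemic shape, the always-tested routes and the source of deaths.
4. **Consistency.** Reconcile section 3 and the 8,000 swabs in Table 2 with Tables 1 and 4. If full testing is intended, remove the rule; the case count in 7.2 then stands.

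The cost is protocol wording and one field on the possible-case lab request form recording whether the person was systematically selected or tested by another route. No extra tests are needed. The stated precision becomes less favourable; if full testing is kept instead, the laboratory load is not reduced.
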